Exclusion Criteria	
 1. Coagulopathy (i.e., international normalized ratio >2.0, activated partial thromboplastin time >50 seconds or platelet count <50,000/mm³) 2. Known bleeding disorder 3. Clinically relevant bleeding as defined by the International Society on Thrombosis and Hemostasis (i.e., Hb decreased ≥2 g/dl in 24 hours, required medical or surgical intervention to restore hemostasis, or in a critical organ system [i.e., retroperitoneum, pulmonary, intracranial or central nervous system]) 4. Admitted for trauma, or neurologic or spine surgery) 5. <60 days from a clinically relevant bleeding as defined above 6. <7 days after trauma or surgery 7. Anticipated surgery within 48 hours after insertion of the CVC 8. Renal failure (i.e., creatinine clearance <30 mL/min) 9. Presence of epidural catheter 9. Currently taking an antithrombotic agent (e.g., LMWH, UFH at therapeutic doses, Coumadin or aspirin) 10. Radiologically documented DVT at the site of insertion of the CVC in the previous 6 weeks 11. Known hypersensitivity to heparin or its components, including pork products 12. History of HIT (i.e., positive serotonin release assay)

	13. Currently pregnant 14. Currently lactating 15. Prior enrollment in the study 16. Limitation of care
Treatment Plan	Eligible subjects will be randomized 1:1 to treatment or control. In subjects randomized to treatment, noxaparin will be given within the first 24 hours after CVC insertion and then every 12 hours (+/-2 hours) thereafter until removal of the CVC. Dosing will start at 0.75 mg/kg for children \leq 2 months old or 0.5 mg/kg (maximum of 30 mg) for older children and will be titrated to a target anti-Xa activity of 0.2-0.5 IU/mL. Safety assessments for bleeding will be completed daily. In subjects randomized to control, no placebo will be given.

STUDY SCHEMA

LIST OF ABBREVIATIONS

AE – adverse event
CADVT – catheter-associated deep venous thrombosis
CAT - Calibrated Automated Thrombogram
Co-I – co-investigator
CRF – case report form
CVC – central venous catheter
DSMB – data and safety monitoring board
DVT – deep venous thrombosis
EDTA – ethylenediaminetetraacetic acid
ETP – endogenous thrombin potential
FDA – Food and Drug Administration
Hb – hemoglobin
HIPAA – Health Insurance Portability and Accountability Act
HIT – heparin-induced thrombocytopenia
ICU – intensive care unit
IL – interleukin
IP – Investigational Product
IRB – institutional review board

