day 2 with an average exposure ratio of about 15% higher than after a single dose. Steady-state enoxaparin activity levels are well predicted by single-dose pharmacokinetics. After repeated subcutaneous administration of the 1 mg/kg twice daily regimen, the steady state is reached from day 4 with mean exposure about 65% higher than after a single dose and mean peak and trough levels of about 1.2 and 0.52 IU/mL, respectively. Based on enoxaparin sodium pharmacokinetics, this difference in steady state is expected and within the therapeutic range.

Metabolism

Enoxaparin sodium is primarily metabolized in the liver by desulfation and/or depolymerization to lower molecular weight species with much reduced biological potency.⁴⁵ Renal clearance of active fragments represents about 10% of the administered dose and total renal excretion of active and non-active fragments 40% of the dose.

Excretion

Following intravenous dosing, the total body clearance of enoxaparin is 26 mL/min.⁴⁵ After intravenous dosing of enoxaparin labeled with the gamma-emitter, 99mTc, 40% of radioactivity and 8 to 20% of anti-Xa activity were recovered in urine in 24 hours. Elimination half-life based on anti-Xa activity was 4.5 hours after a single subcutaneous dose to about 7 hours after repeated dosing. Following a 40 mg subcutaneously once a day dose, significant anti-Xa activity persists in plasma for about 12 hours. Following subcutaneous dosing, the apparent clearance of enoxaparin is approximately 15 mL/min

Drug Interactions

Unless really needed, agents which may enhance the risk of hemorrhage should be discontinued prior to initiation of Lovenox Injection therapy. These agents include medications such as: anticoagulants, platelet inhibitors including acetylsalicylic acid, salicylates. If co-administration is essential, conduct close clinical and laboratory monitoring.

Drug Supply

Specific manufacturer/supplier of Enoxaparin Sodium Injection, USP is up to the discretion of the participating site as long as the product's FDA application has NDA 020164 as the RLD.

Drug Dose

For prophylaxis, enoxaparin is started at 0.75 mg/kg subcutaneously every 12 hours for children \leq 2 months old or 0.5 mg/kg (maximum dose of 30 mg) subcutaneously every

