The dose of enoxaparin will be adjusted to a target anti-Xa activity of 0.2-0.5 IU/mL.^{23, 46, 47} The target anti-Xa activity is a peak level and, therefore, timing is extremely important. The peak level must be drawn 4-6 hours after the dose is actually administered. If the child has other labs ordered which are not time dependent, the other labs should be drawn at the same time the enoxaparin peak level is needed.

Using standard methods, anti-Xa activity will be measured 4-6 hours after a dose at the following time points:

1. After the first 3 doses. If needed, the dose will be adjusted to achieve the target anti-Xa activity. See Table 2 for dose titration.
2. After the 3rd dose of a dose titration until the target anti-Xa activity is reached. Once the anti-Xa activity is within target, the dose will be maintained. See Table 2 for dose titration.
3. Weekly to ensure adequate dosing. Similar dose titration as listed in Table 2 will be done to achieve adequate dosing.

Table 2: Enoxaparin Dosage Titration

Anti-Xa Activity	Enoxaparin Dose Titration	Next Anti-Xa Activity Check
<0.10 IU/mL	Increase dose by 20%	After 3 rd dose.
0.10-0.19 IU/mL	Increase dose by 10%	After 3 rd dose.
0.20-0.50 IU/mL	Keep same dosage	Weekly
0.51-1.00 IU/mL	Decrease dose by 10%	After 3 rd dose.
>1.00 IU/mL	Hold all doses until anti-Xa is 0.3, IU/mL, then decrease dose by 20%	Before next dose and every 12 hours, until anti-Xa <0.3 IU/mL

(Modified from Monagle P, et al. *Chest*, 2001, 119:344S)⁵⁰

Discontinuing enoxaparin

The child will be removed from the study and Enoxaparin will be discontinued for the purposes of the study if ANY the following occur:

1. A clinically relevant bleeding event
 - a. Drop in Hb of ≥ 2 g/dl in 24 hours
 - b. Blood product transfused for the bleeding event
 - c. Required medical or surgical intervention to restore hemostasis
 - d. In a critical organ (*i.e.*, retroperitoneum, pulmonary, intracranial or central nervous system)
2. HIT is diagnosed (*i.e.*, positive serotonin release assay)

Holding the Dose

Enoxaparin will be stopped temporarily if ANY the following occur

1. Coagulopathy (*i.e.*, international normalized ratio >2.0, activated partial thromboplastin time >50 seconds or platelet count <50,000/mm³) develops

2. 12 hours before surgery or invasive procedure
3. In cases of suspected HIT (*i.e.*, an unexplained decrease in platelet count $<50,000/\text{mm}^3$ or by 50% of baseline value in the ICU).

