The child will be off treatment once any of these events occur. Children will be followed for adverse events for 30 hours after the last dose of enoxaparin in the trial. This time period corresponds to 5 half-lives of the drug.⁴⁴ The child will be considered off study after this time period or after the study ultrasound (see below), whichever is later.

OTHER STUDY PROCEDURES

Physical Exam and Medical History

A physical exam of the arms or legs will be performed on all patients at time of enrollment and at the end of treatment. If patient has a CVC in the internal jugular vein, only arms need to be examined. If patient has a CVC in the femoral vein, only legs need to be examined.

The following data collected at the time of admission to the PICU will be extracted from the patient chart and entered into OnCore;

1. CVC characteristics such as time of insertion, length, post insertion interventions and vasopressors administered
2. Components of the Pediatric Risk of Mortality 3 (PRISM 3) score
3. Components of the Pediatric Index of Mortality 2 (PIM) score
4. Patient characteristics including diagnosis, age weight, height, laboratory values, and personal or family history of venous thromboembolism

Ultrasound

Children in the trial will have an ultrasound of the site of insertion of the CVC within 24 hours of removal of the CVC, or earlier upon

1. Discharge from the ICU
2. Radiologic diagnosis of CADVT
3. Start of therapeutic anticoagulation
4. Clinically relevant bleed develops
5. HIT is diagnosed
6. 28 days after insertion of the CVC

The vein will be scanned proximal and distal to the site of insertion. Images in the transverse and longitudinal planes, with and without compression, and with and without color Doppler will be acquired.^{42, 51} Co-I [name] will collaborate with certified sonographers from each ICU to maintain consistent imaging of the central veins. They will be blinded to study-related and clinical information for the trial.

ASSESSING AND REPORTING ADVERSE EVENTS

Definition

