- Unlikely – The AE *is doubtfully related* to the study treatment.

AE does not have temporal relationship to intervention, could readily have been produced by the patient's clinical state, could have been due to environmental or other interventions, does not follow known pattern of response to intervention, does not reappear or worsen with reintroduction of intervention

- Unrelated – The AE *is clearly NOT related* to the study treatment.

The event is clearly due to causes distinct from the use of the study drug, such as a documented preexisting condition, the effect of a concomitant medication, or a new condition which, based on the pathophysiology of the condition, and the pharmacology of the study drug, would be unrelated to the use of the study. All SAEs will be reported to the project manager within 24 hours of the site becoming aware of the event.

Procedure for Reporting Adverse Events

All AEs will be recorded from the time the permission form is signed through 30 hours after the last dose of enoxaparin in the trial. AEs will be recorded on an Adverse Event log at each site and entered in OnCore within 72 hours of the site becoming aware of the event.

All AEs will be reported to regulatory authorities, IRB and investigators in accordance with all local applicable laws and regulations.

AE reporting must also be carried out by each participating site PI, according to their local policy and procedures, to the IRB responsible for oversight of their patients. A copy of the local IRB's acknowledgement should be forwarded to the project manager. All SAEs must be followed until resolution or stabilization. Unanticipated problems involving risk to patients or others and all SAEs related to participation in the study should be promptly reported to the project manager. The project manager shall report all SAEs to the FDA.

All SAEs that are unexpected, which occur any time after the patient has consented up to 30 hours after the last dose of enoxaparin in the trial and are possibly, probably, or definitely related to the research must be reported by the participating site to the project manager within 24 hours of becoming aware of the event. The project manager is responsible for reporting to the FDA (via MedWatch report) according to FDA 21CFR312.32 within 15 calendar days of the event occurring. The project manager will also notify the Yale Human Investigation Committee (within 5 days) and all participating

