Data will be entered into OnCore. De-identified data will then be downloaded in Excel format for statistical analysis, which will be done on a HIPAA compatible, password protected encrypted laptop computer by biostatistician co-I [name] for use. All data entry will be performed by the local study site personnel. All source documentation will be retained at the local study site per local site regulations and monitored during regularly scheduled monitoring visits.

TRIAL FLOW CHART

Procedure	Screening Period	Treatment Period	End of Study CVC Removal
Parental permission/assent	X		
Review of eligibility criteria	X		
Randomization	X		
Medical record review and data collection from ICU admission		X	
Physical exam of arms or legs, and for sexual maturity rating ^a		X	X
Administration of enoxaparin ^b		X	
Measure Anti-Xa activity ^c		X	
Ultrasound ^d			X
Bleeding assessment ^e		X	X
Assess for AEs ^{e,f}	X	X	X
CBC with differential ^g		X	
Renal function tests (BUN, creatinine) ^g		X	
Serum aminotransferases ^g		X	
Stool occult bleed ^h		X	
Blood collection for correlatives		X ⁱ	X
Urine collection for correlatives		X ⁱ	X

a: At time of enrollment for physical exam of arms or legs (if patient has a CVC in the internal jugular vein, only arms need to be examined; if the CVC is inserted in the femoral vein, only legs need to be examined), and at any time during the admission for the sexual maturity rating.

b: 1st dose <24 hours after insertion of the CVC, then every 12±2 hours until CVC removal. Only for subjects randomized to the treatment arm.

c: Anti-Xa activity will be measured 4-6 hours after the 3rd dose, then every 3rd dose until target is achieved. After target achieved, measurement is weekly.

d: Within 24 hours of removal of the CVC, or earlier upon discharge from the ICU, radiologic diagnosis of CADVT, start of therapeutic anticoagulation, clinically relevant bleed develops, HIT is diagnosed, or 28 days after insertion of the CVC

e: Daily.

f: Starting from time permission form is signed until 30 hours after the last dose of enoxaparin in the trial.

g: Within 48 hours of enrollment and at least weekly ± 2 days, thereafter.

h: If clinically indicated as determined by the site PI.

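### Adverse-event recording ends on a dosing clock that controls do not have, and the protocol contradicts itself on whether a treated child with a bleed or HIT leaves the study

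*Combined protocol and SAP*

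**What the plan says.** **AE window.** Procedure for Reporting Adverse Events gives the rule: "All AEs will be recorded from the time the permission form is signed through 30 hours after the last dose of enoxaparin". Footnote f of the Trial Flow Chart repeats it: "Starting from time permission form is signed until 30 hours after the last dose of enoxaparin in the trial". Duration of Therapy has the same 30 h period and justifies it: "This time period corresponds to 5 half-lives of the drug". None of these places has a version for controls. The Treatment Plan in the Trial Summary says of the control arm: "In subjects randomized to control, no placebo will be given".

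**Leaving the study.** Duration of Therapy adds a general rule, "The child will be considered off study after this time period or after the study ultrasound", taking the later of the two. Discontinuing enoxaparin has a different rule for a clinically relevant bleed or diagnosed HIT: "The child will be removed from the study and Enoxaparin will be discontinued for the purposes of the study".

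**Other relevant text.** The Ultrasound section and flow-chart footnote d schedule the scan in both arms by catheter removal or an earlier listed event. A clinically relevant bleed and HIT are both on that list. Bleeding Assessment has its own daily schedule. Outcome Measures names clinically relevant bleeding, confirmed HIT and mortality as safety outcomes. It fixes their start at catheter insertion and gives no common end. For half-life, Excretion gives "4.5 hours after a single subcutaneous dose to about 7 hours after repeated dosing".

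**The concern.** A between-arm comparison of safety needs a window that opens and closes by rules both arms can meet. Here the closing rule is the last dose of a drug that half of the 100 children never receive. A child randomised to enoxaparin but never dosed has the same problem. Sites must then improvise an end for controls, and the AE counts by arm may cover different lengths and different parts of the stay. The same anchor governs expedited reporting of unexpected, related serious events.

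The removal wording is a second, separate problem. It sits under a heading that can apply only to treated children. If a site takes it literally, a treated child who bleeds or develops HIT may miss the ultrasound that defines the primary outcome, while a control who bleeds is still scanned.

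**Working it through.** **1. The end of the control window.** The written end is last dose + 30 h. Controls have no last dose, so it is undefined for them. The off-study rule takes the later of the 30 h period and the ultrasound. With the first term missing, only the ultrasound remains. That is an inference; no section states it.

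**2. Windows around an ordinary catheter removal.** Inputs: dosing every 12±2 h until removal (Treatment Regimen with Enoxaparin), so the last dose falls 0 to 14 h before removal if doses are on schedule; ultrasound within 24 h of removal (Ultrasound).
- Treated: end after removal = 30 − gap, which runs from 30 − 14 = 16 h to 30 − 0 = 30 h.
- Control (inferred): 0 to 24 h after removal.
- Treated minus control: from 16 − 24 = −8 h to 30 − 0 = +30 h.

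The treated window is usually longer in this situation, but not always.

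**3. Held doses.** Holding the Dose stops enoxaparin temporarily for coagulopathy, before procedures and for suspected HIT. None of these ends the study period. If dosing never resumes while the catheter stays in, the literal AE window closes 30 h after the last dose. The child remains on study until the ultrasound. Here the treated window is too short, so the error can run in either direction.

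**4. The removal rule beside the other rules, for a bleed or HIT.**

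| Section | Consequence |
|---|---|
| Discontinuing enoxaparin | Enoxaparin stops and the child leaves the study |
| Duration of Therapy | Treatment ends; AE follow-up continues for 30 h; off study at the later of that and the ultrasound |
| Ultrasound; flow-chart footnote d | The event triggers the study ultrasound |

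All agree that enoxaparin stops. They disagree on whether the child stays under observation.

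Size, using the protocol's 2.3% clinically relevant bleeding rate on LMWH prophylaxis (Minimizing Risks) and 100/2 = 50 children per arm: 50 × 0.023 = 1.15 children. The protocol gives no HIT rate for this population, so HIT is not counted. If those children had the untreated CADVT rate of 0.18 (an assumption), the expected number of CADVT lost is 1.15 × 0.18 ≈ 0.2.

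**5. The five half-lives statement (minor).** Reproducing the plan's figure: 30 h / 5 = 6 h, a half-life that the protocol states nowhere. From Excretion:
- Single dose, 4.5 h: 5 × 4.5 = 22.5 h. Thirty hours covers 30/4.5 = 6.67 half-lives, leaving 0.5^6.67 ≈ 1.0%.
- Repeated dosing, about 7 h: 5 × 7 = 35 h. Thirty hours covers 30/7 = 4.29 half-lives, leaving 0.5^4.29 ≈ 5.1%, against 0.5^5 ≈ 3.1% at five.

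This trial doses repeatedly, so the second line is closer to its use. The same 30 h decides attribution of bleeding to the drug in Minimizing Risks.

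**The case against.** Much of the follow-up does not depend on dosing, and this part of the objection stands. The ultrasound follows catheter removal or listed events in both arms. Bleeding is assessed daily: in the flow chart its row carries only footnote e, while the 30 h footnote belongs to the AE row. A reader might infer that all follow-up is tied to exposure, or that the bleeding comparison is biased. The documents support neither; the defect lies in AE recording.

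A reader might also compare a treated child whose drug stops on day 2 with a control observed for the 6-day mean catheterisation, and conclude that much of the at-risk time is lost. That comparison fails for permanent stops, because those events also trigger the ultrasound in either arm. It fits only a hold that is never reversed.

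A reader might take the removal sentence as planned, informative loss from the primary outcome. The Ultrasound section and footnote d say the opposite, so this is a contradiction between sections and not settled attrition. Nor should the 5.3% in Minimizing Risks be used as a treated-arm bleeding rate; there it sets a notification count over all 100 children.

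Finally, 30 h lies inside the 22.5 to 35 h implied by the quoted half-lives. The pharmacokinetic data are from adults where a population is named, and Duration of Therapy cites a different source from Excretion. The 30 h figure cannot be called wrong outright.

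What survives is that no section states an AE end for controls, and that the sections disagree on who leaves the study.

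**Conclusion.** The point holds for AE recording and for the removal wording, and it should be fixed. Followed as written, the AE rule cannot be applied to controls or to never-dosed children. The best available inference gives windows ending 16 to 30 h after removal in treated children against 0 to 24 h in controls, assuming on-schedule dosing up to removal. An unrestarted hold shortens the treated window instead, so the net direction of any bias is unknown. HIT and deaths are affected to the extent that they are captured through AE recording; the protocol does not say whether mortality has another source. Bleeding is less affected.

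The conflict over removal could cost primary-outcome data in the enoxaparin arm only, for about 1 of 50 children at a 2.3% bleeding rate, and only at sites that follow Discontinuing enoxaparin over the other sections. The half-life statement is a minor inconsistency: it is exact only at an unstated 6 h.

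**What to change.** 1. Define one AE and safety-outcome window for both arms. Start it at permission or randomisation and end it a fixed interval after the common end-of-study-period event (catheter removal or the earlier listed events). In treated children it should not end before the post-last-dose period is over. Use it in Duration of Therapy, Procedure for Reporting Adverse Events, Outcome Measures and flow-chart footnote f.
2. Reconcile Discontinuing enoxaparin with Duration of Therapy, Ultrasound and footnote d. Stopping study drug should be distinguished from leaving the study, so that ultrasound and AE data are kept for every randomised child. This concerns data collection and changes no stopping criterion.
3. Reconcile the five half-lives statements in Duration of Therapy and Minimizing Risks with the half-lives in Excretion, or cite the half-life actually used. Which value applies is for the sponsor to settle.

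The cost is protocol wording, date logic in the case report form, and a few more hours of chart review per child.
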